2.5.5 Efficacy Analysis

- Ulcer improvement**

A table showing the number of subjects completely healed in the target ulcer will be provided at up to 6 months, > 6 months to 12 months, from >12 months to 18 months. If available, the number of subjects with at least 20% reduction in bi-dimensional size (by measuring largest diameters) will be provided. The reduction in bi-dimensional size will be calculated by taking the product of the largest diameters for each baseline and postbaseline measurement, then subtracting the baseline result from the postbaseline result.

- Ischemic Rest pain (of the index leg) using a 10 cm VAS scale**

Rest pain severity will be assessed at the specified predetermined time points. Rest pain severity will also be assessed prior to surgical revascularization or major amputation (of the index leg). A table showing the number of subjects reduced by ≥ 20 mm from baseline in VAS score will be provided at up to 6 months, > 6 months to 12 months, from >12 months to 18 months. Summary statistics will be provided for baseline and change from baseline for each visit and LOCF. One sample t-test for change-from-baseline will be performed. If death occurs, the worst score prior to death instead of last observation will be carried forward.

- Hemodynamic Measurements**

Summary statistics will be provided for baseline and change from baseline for hemodynamic parameters (right/left brachial systolic pressure, ankle systolic pressure measured at dorsalis pedis and posterior tibial, toe systolic pressure, calculated ABI, and calculated TBI) by visit. At each visit, only subjects who have a non-missing value at both baseline and the specific visit will be summarized. Two-sided one-sample t-test will be performed for each visit and LOCF.

- Subjects with any worsening CLI event of index leg**

A summary table and listing of worsening CLI-related events of the index leg including any new or worsening events, worsening rest pain, new ulcer or worsening ulcer, new or worsening wound infection, peripheral vascular intervention, complication of a peripheral vascular intervention, cellulitis, and amputation due to worsening CLI will be provided.

- Subjects who either died, had MI, Stroke, revascularization (by surgical bypass, by endovascular intervention, by hybrid procedure), major amputation, or all-cause death**

A summary table including counts and percentages and a listing will be provided for these parameters for the following time periods: up to Month 6, 0 to Month 12, and 0 to Month 18.

As a supplemental analysis, time to major amputation or death will be performed, and the Kaplan-Meier (KM) estimates with 2-sided 95% confidence interval using Greenwood's formula will be computed up to the end of the study and plotted. If a subject undergoes major amputation followed by death, it will be counted as an event. If a subject does not experience major amputation or death, the subject will be censored at the date of last contact as recorded on the CRFs.

- **Shift from baseline in Rutherford classification**

Shift from baseline in Rutherford classification will be summarized by study visit.

- **Quality of life (QoL)**

Quality of life (QoL) measurements will be assessed using the disease-specific vascular Quality-of-Life questionnaire (VascuQol). The VascuQol contains 5 domains (pain, symptom, activities, social, and emotional functioning), and responses are scored from 0 (lowest QOL imputed after death) to 7 (best QOL, maximum health). Responses are averaged for composite overall and domain-specific scores, giving equal weight to each question and domain. Subjects' data after revascularization or major amputation will be included in the analysis. However, after death, subjects will be scored as 0. For the effect of treatment on individual domains, pain, symptoms, and activity will be considered the most important of the 5 domains.

Summary statistics will be provided for baseline and change from baseline by visit for each score including total and domain scores. At each visit, only subjects who have a non-missing value at both baseline and the specific visit will be summarized, and two-sided one-sample t-tests for the change-from-baseline will be performed for each visit and LOCF.

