3.4. Administration of Study Product

Study product will be administered to subjects who were confirmed eligible by the Principal Investigator (eligibility will be confirmed by an entry committee) and whose CLI is stable (see Exclusion Criteria Section 3.3, item #1).

The study product will be administered by eight (8) intramuscular injections delivered to the index leg (see Section 3.2 Inclusion criteria for definition of index leg) at each dosing visit (see Table 1 Dosage Regimen above). For each of the 8 injections, 3 mL of AMG0001 will be injected in about 3 seconds. The precise anatomical location for study product injections will be based on vascular anatomy. The site will receive a detailed schema from the above entry committee indicating where the injection sites should occur. Duplex scanning must be used during the injection procedure to further clarify the injection sites.

Subjects will not be eligible to receive the subsequent doses of study product if a major amputation of the index leg has occurred. If the subject has been revascularized in the index leg, the Investigator should ensure that the subsequent doses of study product are not administered less than 1 month post-revascularization.

Analgesics may be administered prior to treatment injections. Local anesthetics applied to the skin are recommended. An anti-anxiety agent may be administered pre-dose to relieve any anxiety surrounding treatment procedures. Administration of analgesics is at the discretion of

the Investigator, but cannot be given to the subject prior to VAS pain scale measurement or Quality of Life (VascuQol Questionnaire) measurements. All analgesics given prior to injection should be accurately recorded on the appropriate Concomitant Medication CRF.

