4.4. Concomitant Medications

Concomitant medication and the indication for its use must be clearly documented and recorded in the source documentation and CRF for each subject. Any medications taken from the date informed consent is signed and onward should be documented in the CRF.

The use of analgesic medications during the study should be carefully recorded. Investigators should refrain from making changes in the subject's use of analgesic medications after the baseline visit, unless the subject's medical condition warrants changes to their treatment. Changes in the use of analgesic medications after the baseline visit could confound the interpretation of endpoint assessments.

Topical wound medications must be captured as concomitant medications in the CRFs. **Wound care products such as Regranex® (rhPDGF), Apligraft®, Dermagraft®, Oasis®, as well as any other skin equivalents or topical growth factors are excluded for use during this trial. Hyperbaric oxygen (HBO) treatment is also excluded.**

All subjects should be on a statin and an anti-platelet agent (e.g., clopidogrel, ticlopidine, aspirin, etc.) as part of their standard of care, unless contraindicated. Subjects for which these agents are contraindicated must have the restriction reason recorded in their source documentation and CRF.

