8.1.2. SAEs Associated with Worsening CLI

Serious Adverse Events relating to the worsening of CLI that occur in the index limb such as gangrene, cellulitis or osteomyelitis, are related to the study disease and are symptoms/signs of progression of study disease will not be recorded as serious adverse events (unless the speed or extent of the symptoms/signs are unexpected based on the natural history or bear a strong temporal relationship to the study product as determined by the Investigator). Data on the subject's CLI status of the index limb will be recorded in detail on non-AE CRFs and is not required to be documented as an SAE. Frequently worsening of CLI may lead to hospitalization followed by local or systemic treatment or surgical intervention (minor amputation, surgical revascularization or major amputation). The entries for the above events will be made in the CLI section of the CRF. However, in the case of serious intercurrent illness or systemic complications like septicemia, multi-organ failure, or pneumonia, these events will be captured in the AE or SAE section of the CRF.

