9. EVALUATIONS AND STATISTICAL METHODS

9.1. Evaluations

The following evaluations relating to tolerability, safety and clinical benefit will be made:

1. Adverse events (AEs) suspected to be related to injections of HGF plasmid
2. Discontinuations related to adverse effects from the injections of HGF plasmid
3. All AEs up to Month 3, Month 6, Month 12, and Month 18
4. Serious adverse events (SAEs) up to Month 3, Month 6, Month 12, and Month 18
5. Number of deaths and cause over the 18 month period up to Month 3, Month 6, Month 12, and Month 18
6. Number of subjects in whom the largest ulcer healed completely or gets smaller (photo confirmation) at 6, 12 and 18 months (cumulative)
7. Number of subjects in whom rest pain (based on the 100 mm VAS scale) reduces by 20 mm or more or was completely relieved at 6, 12 and 18 months (cumulative)
8. Change in VascuQol Questionnaire (QOL) score compared to the baseline at 6, 12 and 18 months
9. Number of subjects revascularized (bypass or endovascular intervention) up to Month 3, Month 6, Month 12, and Month 18
10. Number of subjects with minor and number of subjects with major amputations (at or above the ankle) up to Month 3, Month 6, Month 12, and Month 18

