9.2.2. Statistical Analysis for Efficacy and Safety

Categorical data will be summarized by the use of frequency tables showing the number and percentage of subjects falling within a particular category by visit, and detailed line listings of subjects will be provided.

Continuous data will be summarized by reporting number of observations, mean, standard deviation (SD), median, minimum and maximum by visit. Summary statistics will be provided for baseline and the change (with percent change) from baseline. A one-sample t-test will be performed on within group change-from-baseline for individual time point (Months 6, 9, 12, 15, and 18 with last observation data (assessed prior to intervention or worse score for deaths) carry-forward (LOCF)).

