2.4.2 Missing Data

For endpoints involving the VascuQoL assessment, non-missing data after revascularization or major amputation will be included in analysis, and missing values for subjects who are dead at the time point of interest will be scored as 0.

For the Visual Analogue Scale (VAS), each subject’s data after revascularization or major amputation will be imputed using the value of the last available assessment prior to intervention, and the worst score available will be imputed for assessments after death.

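### The ulcer-healing count ignores prior index-leg revascularization, and the SAP does not classify a target ulcer removed by amputation

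*SAP*

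**What the plan says.** SAP 2.5.5, under ulcer improvement, states: "A table showing the number of subjects completely healed in the target ulcer will be provided at up to 6 months". It goes on to the periods after Month 6 up to Month 12 and after Month 12 up to Month 18. A second count, of ulcers at least 20% smaller, is promised only if size data are available. Protocol 9.1, item 6, lists the evaluation as "Number of subjects in whom the largest ulcer healed completely or gets smaller (photo confirmation) at 6, 12 and 18 months (cumulative". Neither text mentions intervention on the index leg.

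SAP 2.4.2 does address intervention for two other endpoints, and treats them in opposite ways. For VAS rest pain, each subject's "data after revascularization or major amputation will be imputed using the value of the last available assessment prior to intervention". For VascuQoL, "non-missing data after revascularization or major amputation will be included in analysis". There is no entry for the ulcer.

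Follow-up continues after intervention. Protocol 3.4 says "If the subject has been revascularized in the index leg, the Investigator should ensure that the subsequent doses of study product are not administered" within a month of the procedure, which means that dosing may resume later. Protocol 4.9 has ulcer and leg photographs taken through Month 18. Under Protocol 5.18 the investigator inspects the largest ulcer at each visit, a healed ulcer is looked at again after two weeks, and an outside physician confirms the healing.

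**The concern.** Revascularization is itself a treatment for an ischemic ulcer, and the protocol foresees it. Section 4.7 says that no necessary intervention will be withheld. Section 8.1.2 says that worsening CLI may often lead to hospital admission and surgery. SAP 2.5.5 plans a table of bypass, endovascular and hybrid procedures. A subject whose disease progressed far enough to need such a procedure can then appear in the efficacy table as an ulcer success.

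There is no control arm to offset this. Protocol 1.1 names ulcer healing among the effects already seen with AMG0001, so the count is likely to be read as evidence of benefit. It would also stand beside the VAS responder count, over the same three periods, where post-intervention values are replaced. The two results for one subject would then answer different questions, and the table would not say so.

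**Working it through.** The plan states no healing rate, intervention rate or power figure, so there is nothing to reproduce. The check compares the rules and then does arithmetic for scale.

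**1. Rules after index-leg revascularization**

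| Endpoint | Type | Rule | Place |
|---|---|---|---|
| VAS rest pain | score and responder count | last value before intervention | SAP 2.4.2 |
| VascuQoL | score | observed values kept | SAP 2.4.2, 2.5.5 |
| Target ulcer healed | yes/no count | none stated | SAP 2.5.5, Protocol 9.1 |

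**2. Does a general rule fill the gap?** Protocol 9.2.2 describes a one-sample t-test on change from baseline "with last observation data (assessed prior to intervention or worse score for deaths) carry-forward (LOCF". That clause belongs to a test on continuous change and does not reach a count of subjects. The checks in Protocol 4.9 and 5.18 establish that an ulcer has closed and stayed closed, not what closed it. SAP 2.5.7 mentions subjects who left the study because of revascularization, which would end their ulcer data. No section requires that exit, and Protocol 3.4 provides for continued dosing.

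**3. One subject traced through the plan.** The ulcer is open at Month 6, the index leg is bypassed before Month 9, and the ulcer is closed and confirmed by Month 12. VAS at Month 12 is the pre-bypass value. The ulcer is counted as healed in the second period.

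**4. Size.** Let n be the denominator, x the subjects healed with no prior intervention, and k those healed only after index-leg revascularization. The default result is (x + k)/n. The result without prior intervention is x/n. The difference is k/n, which is never negative. For k = 1:

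- n = 10: 1/10 = 10 points
- n = 8: 1/8 = 12.5 points
- n = 5: 1/5 = 20 points. Five subjects with ulcers is an assumption. The documents give no number, but Rutherford 4 subjects are eligible, so not everyone need have an ulcer.

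Illustrations with exact (Clopper-Pearson) 95% intervals, the observed counts being assumed:

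| n | Default count | Without the one post-intervention case |
|---|---|---|
| 10 | 4/10 = 40% (12.2 to 73.8) | 3/10 = 30% (6.7 to 65.2) |
| 8 | 3/8 = 37.5% (8.5 to 75.5) | 2/8 = 25% (3.2 to 65.1) |

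**5. How likely is at least one such case?** Let q be the chance that an enrolled subject has a target ulcer that closes only after index-leg revascularization. The documents do not give q. Assuming independent subjects, the chance of one or more is 1 − (1 − q)^n:

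| Assumed q | n = 8 | n = 10 |
|---|---|---|
| 5% | 34% | 40% |
| 10% | 57% | 65% |
| 20% | 83% | 89% |
| 30% | 94% | 97% |

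**6. Amputation.** No arithmetic applies. Neither document says what healing means for an ulcer on a part that has been removed.

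**The case against.** The strongest reply is that the effect is small and visible. SAP 2.4.1 calls all testing descriptive and exploratory, and the primary objectives are feasibility, tolerability and safety. Every table has a listing, and interventions have their own. With 8 to 10 subjects, anyone can match a healed ulcer to a procedure. The shift of one subject is also small beside intervals about 60 points wide. All of this stands and limits the weight of the point. It does not correct the headline count, where the error runs in one direction only.

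Second, the SAP openly keeps post-intervention data for VascuQoL, so counting healing regardless of intervention follows one of its own two approaches. That also stands. The difference from VAS is an unexplained inconsistency, not a contradiction. A reader might infer that VAS is frozen because intervention treats the symptom, but the SAP gives no reason.

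Third, every subject enters with no endovascular option and with no option or a poor one for bypass, so later revascularization may be uncommon. Its frequency is unknown. The plan still provides for it, including endovascular procedures.

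Three stronger readings are tempting, and the documents do not support them:

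- A reader might infer that an ulcer removed by a minor amputation is counted as healed. No section says so. Direct inspection, photographs, the two-week recheck and outside confirmation might well reject such a site. The classification is unstated, no more than that.
- A reader might infer that minor amputation is ignored in the analysis. Protocol 9.1, item 10, counts it, and the worsening-CLI table in SAP 2.5.5 includes amputation due to worsening CLI. What is missing is a link to the ulcer count.
- A reader might extend the point to the wound products and hyperbaric oxygen excluded by Protocol 4.4. Their use would be a protocol deviation. SAP 2.5.2 lists major deviations and SAP 2.5.4 lists concomitant medications, so this is a separate matter.

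**Conclusion.** The point holds for revascularization. Followed as written, the plan counts an ulcer that closes after index-leg revascularization as ulcer improvement. For amputation the finding is narrower: the SAP leaves a removed target ulcer unclassified.

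Each ulcer closed after revascularization adds 10 to 12.5 points at n = 10 to 8, or 20 points if only 5 subjects have ulcers (assumed). How many such cases will occur cannot be derived from the documents. The conclusion assumes that revascularized subjects stay in follow-up, as Protocol 3.4 allows. The primary objectives are not affected. This is a change worth making to a secondary, descriptive result, not a flaw that undermines the study.

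**What to change.** In SAP 2.5.5, report two rows for each period:

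- **(a) Main count:** target ulcer healed with no prior index-leg revascularization (surgical, endovascular or hybrid) and no prior amputation involving the target ulcer.
- **(b) Beside it:** target ulcer healed regardless of intervention.

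State that a target ulcer removed by minor or major amputation is not counted as healed in either row. Apply the same split to the count of ulcers at least 20% smaller, if size data are available.

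Showing both rows avoids imposing a single strategy: a reader who prefers the approach used for VascuQoL has row (b). Protocol 4.7 and 4.9 already require intervention details on the CRF, and Protocol 5.15 requires photographs before a planned surgical revascularization or major amputation. The cost is a short addition to the SAP and one table row. The downside is that the main count may be slightly less favourable. Clinical management does not change.

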4.9. Assessment of CLI and Ulcer Photography and Tracings

For study entry, the subject must be evaluated for clinical evidence of CLI according to the definition of the study population for this protocol found in Section 3.1 Study Population.

The Investigator must assign a baseline status to the subject's peripheral vascular disease based on the status of the index leg using the Rutherford Classifications (see Appendix C). In case of Rutherford Category 4 and Rutherford Category 5, the Principal Investigator must make sure that the inclusion criteria for subjects with Rutherford Category 4 and Rutherford Category 5 are

strictly followed for the subjects to be eligible to enter the study. (See Section 3.1 Study Population)

During the study, specific information on the subject's CLI status will be documented on the CRF and in the source documentation including information on ulcers/gangrene, rest pain, debridement/wound care, infection treatment, hospitalizations, minor and major amputations, revascularization by surgical bypass, etc.

In order to accurately assess ulcer size, the ulcer (s) must be cleaned and debrided to remove necrotic tissue, eschar, and callouses prior to photographs and ulcer tracings, as per the wound care guidelines (see Appendix D).

During Screening, ulcer photography and tracings of the largest ulcer (with ulcer debridement occurring prior to photography and tracing) must be performed and used as one of the evaluations to be made to confirm CLI stability for entry into the study. Ulcer photography at screening should include one photograph of the largest ulcer on the index leg and additional photographs of the index leg that capture the foot and lower leg to confirm the location of the largest ulcer, as well as all additional ulcers (and gangrene) and the overall status of the index leg at screening.

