Prior to dosing on Day 0, ulcer photography and tracing of the largest ulcer as at Screening (with ulcer debridement occurring prior to photography and tracing) will be completed again for establishing stability of the largest ulcer and of additional ulcers on the index leg prior to randomization. Ulcer photographs and photographs of the index leg will be taken at each visit (Day 14 through Month 18) and prior to any planned intervention of the index leg (surgical revascularization or major amputation). If the largest ulcer on the index leg heals during the study period, the ulcer must be re-evaluated 2 weeks after healing to confirm it has remained healed for a period of 2 weeks (this will require an additional visit to the site). Ulcer healing will be confirmed later via photographs by the study entry committee. *Ulcer and leg photographs must continue to be taken throughout the study period, regardless of the healing of the largest ulcer.*

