Physical Examination	X(1)	X(2)	X(2)	X(2)	X(1)	X(2)	X(2)	X(2)	X(1)	X(1)	X(2)	X(2)	X(1)	X(2)	X(2)	X(2)	X(2)	X(1)	X(1)	
Peripheral Vascular Intervention History/Update	X(3)*	X(3)	X(3)	X(3)	X(3)	X(3)	X(3)	X	X(3)	X(3)	X(3)	X(3)	X(3)	X(3)	X(3)	X(3)	X(3)	X	X	
CLI Assessment (7)	X*	X	X	X	X	X	X	X	X	X	X	X	X	X	X	X	X	X	X	
Ulcer Tracings	X(4)*																			
Ulcer Photography (7)	X(4)*	X(6)	X(6)	X(6)	X(6)	X(6)	X(6)	X(6)	X(6)	X(6)	X(6)	X(6)	X(6)	X(6)	X(6)	X(6)	X(6)	X(6)	X(6)	
Retinopathy Examination															X				X	
Study product Administration	X	X	X	X	X	X	X	X	X	X	X	X	X	X	X	X	X			
Injection Site Photography	X	X	X	X	X	X	X	X	X	X	X	X	X	X	X	X	X			
Angiogram Assessment (7)															X					
TcPO2 (7)	X(3)			X(3)					X(3)	X(3)					X(3)			X	X	
Hemodynamic Measurements (7)	X(3)*			X(3)					X	X(3)					X(3)			X	X	
QOL (EQ-5D5L) (7)	X(3)*			X(3)					X	X(3)					X(3)			X	X	
VAS (pain scale) (7)	X(3)*			X(3)					X	X(3)					X(3)			X	X	
Urine Pregnancy	X(5)			X(5)						X(5)					X(5)					
Hematology, Chemistry, & CBC	X(3)			X(3)					X	X(3)					X(3)			X	X	
Urinalysis Collection	X(3)			X(3)					X	X(3)					X(3)			X	X	
Anti-HGF Antibodies Assay	X(3)			X(3)					X	X(3)					X(3)			X	X	
Adverse Events Review (7)	X	X	X	X	X	X	X	X	X	X	X	X	X	X	X	X	X	X	X	
Concomitant Medication Review (7)	X	X	X	X	X	X	X	X	X	X	X	X	X	X	X	X	X	X	X	

* Investigator must confirm stability of CLI prior to dosing between Day -2 and Day 0. These items must be submitted to the Adjudication Committee as a third party confirmation of CLI stability.

(1) Complete physical exam should be performed. If a dosing visit, perform prior to dosing.

(2) Abbreviated physical exam should be performed. If a dosing visit, perform prior to dosing.

(3) Prior to dosing.

(4) Stability of CLI (≥ 2 weeks between the screening and the Day 0 assessments) and subject's ulcers should be confirmed prior to dosing, the subject must have a photo of the largest ulcer on the index leg as well as a photo(s) of the entire index leg to show all ulcer/gangrene locations. Tracings should be taken of the largest ulcer on the index leg only. These must be submitted to the Adjudication Committee. Debridement must be performed prior to these evaluations;

(5) Urine pregnancy tests will be performed prior to dosing on all women aged 55 years or less. For women who have been determined as premenopausal and are not surgically sterile, per the study requirements, will continue with the scheduled urine pregnancy testing throughout the course of the study.

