
(6) Photos of largest ulcer on the index leg as well as a photo or photos (if necessary) of the entire index leg to show all ulcer/gangrene locations. Debridement should be performed prior to these evaluations;

(7) Procedure must be performed prior to a planned interventional treatment (revascularization or amputation) while on study.

** For the purposes of this study a month is defined as 30 days. Days 14, 28 and 42 are calculated from either Day 0, Month 3, Month 9 or Month 12. All (non-dosing) follow-up visits should be calculated based on Day 0/Baseline.

Table 4: Schedule of Sample Collection for the Serum HGF Protein & PCR for HGF Plasmid Assays

Schedule of Sample Collection for the Serum HGF protein & PCR for HGF Plasmid Assays																	
PROCEDURE	Dosing Visit: First Cycle	PK Sampling Visit	Dosing Visits: First Cycle							Follow Up Visit	Dosing Visits: Second Cycle				PK Sampling Visit	Dosing Visit: Second Cycle	Follow Up Visit
Time	Day 0	Day 4	Day 14	Day 28	Day 42	Month 3	Month 3 Visit + 14 Days	Month 3 Visit + 28 Days	Month 3 Visit + 42 Days	Month 6	Month 9	Month 9 Visit + 42 Days	Month 12	Month 12 Visit + 4 days	Month 12 Visit + 42 Days	Month 15	
Vist Window	Baseline	0	± 2 days	± 2 days	± 3 days	± 7 days	± 2 days	± 2 days	± 2 days	± 7 days	± 7 days	± 2 days	± 7 days	0	± 2 days	± 7 days	
Serum HGF protein Assay	X*	X	X*	X*	X*	X*			X*		X*		X*	X			X
PCR for HGF plasmid DNA Assay	X*	X	X*	X*	X*	X*	X*	X*	X*	X	X*	X*	X*	X	X*	X*	X

*At Dosing Visits (indicated by the shaded columns), two (2) samples should be drawn one pre-dose and a second drawn four hours post-dosing.

** The first 5 subjects who were randomized and received test medication will have blood samples drawn for PK 4 days following their Month 9 Visit.

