The subject should remain in a supine position to receive all injections. For each of the 8 injections, 3 mL of AMG0001 will be injected in about 3 seconds with a 21G needle. Each of the injection sites will be marked with a tattoo pen. At completion of study product administration, photographs must be taken of the injection sites. In the injection site photo, a ruler should be placed alongside the index leg to assist with the accuracy of the subsequent injection site locations in case one or more of the tattoo pen marks cannot be seen.

The subject must remain in a supine position for 15 minutes post injections. The time of the study product administration should be noted in the subject's source documentation.

5.3.3. Post-Dosing Procedures: Day 0

Adverse events, if any, should be documented during and subsequent to the injection of the study product.

A blood sample will be obtained four (4) hours after the study product injections are completed for measurement of serum HGF protein and HGF plasmid DNA

Subject will be discharged from the clinic when clinically stable.

5.4. PK Sampling Visit: Days 4

A blood sample will be obtained at the Day 4 Visit to measure the serum HGF protein and the HGF plasmid DNA. In the first 5 subjects studied, similar sampling will occur 4 days after the Month 9 Visit.

5.5. Dosing Visit Study Procedures: Days 14 (\pm 2 days), 28 (\pm 2 days), and 42 (\pm 2 days)

Pre-Dosing Procedures: Days 14 (\pm 2 Days), 28 (\pm 2 Days), and 42 (\pm 2 Days)

1. Medical History review
2. Abbreviated Physical Examination
3. Peripheral Vascular Intervention Update
4. Assessment of CLI
5. Ulcer/gangrene and Index Leg Photography (after debridement, if necessary)
6. Collect Pre-dose blood samples for the Serum HGF protein assay and the PCR for HGF Plasmid DNA assay
7. Adverse Event review
8. Concomitant Medication review
9. Weight and Vital Signs assessment

Dosing Procedures: Days 14 (\pm 2 days), 28 (\pm 2 days), and 42 (\pm 2 days)

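### No scaled ulcer measurement is specified after Day 0, so the SAP's count of ulcers that shrink by at least 20% has no defined data source

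*SAP*

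**What the plan says.** **Planned counts.** Protocol 9.1 item 6 lists: "Number of subjects in whom the largest ulcer healed completely or gets smaller (photo confirmation) at 6, 12 and 18 months (cumulative". It gives no size threshold and no measuring method. SAP 2.5.5 adds a numerical version: "If available, the number of subjects with at least 20% reduction in bi-dimensional size (by measuring largest diameters) will be provided". The SAP takes the product of the largest diameters at baseline and after baseline, and subtracts the first from the second.

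**Planned measurements.**

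- Screening (protocol 4.9): "During Screening, ulcer photography and tracings of the largest ulcer (with ulcer debridement occurring prior to photography and tracing) must be performed".
- Day 0 (protocol 4.9): "Prior to dosing on Day 0, ulcer photography and tracing of the largest ulcer as at Screening" is to be completed again, to establish stability.
- After Day 0 (protocol 4.9): "Ulcer photographs and photographs of the index leg will be taken at each visit (Day 14 through Month 18".
- Content of the later pictures (protocol Table 3, footnote 6): "Photos of largest ulcer on the index leg as well as a photo or photos (if necessary) of the entire index leg".

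The tracing row of protocol Table 3 has a single entry, at Day 0. Footnote (4) to that entry says which ulcer is traced: "Tracings should be taken of the largest ulcer on the index leg only".

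**Scale.** The protocol asks for a ruler in one kind of picture only. Section 5.3.2 says: "In the injection site photo, a ruler should be placed alongside the index leg". Section 5.5 and Appendix A repeat this for injection sites. No instruction on ulcer photographs mentions a ruler, a scale marker or a camera distance.

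**The concern.** A percentage reduction in diameters needs two measurements on a common scale. The plan specifies photographs at both times but requires a scale at neither, and it specifies a tracing only before treatment. Nor does it say who reads the diameters, or from what.

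Followed as written, the 20% table may be empty. If diameters are instead read from pictures of unknown scale, differences in camera distance could help decide who counts as improved. The protocol plainly cares about ulcer size: section 4.9 requires debridement before pictures and tracings so that size can be assessed accurately. The pilot also exists to confirm that the study activities are feasible before the phase 3 study, so a gap between a planned count and its data is worth closing here.

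**Working it through.** The documents give no sample size, power or effect size for this endpoint, so there is no figure of the plan's own to reproduce. The check has two parts.

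**1. Tracing and photography, visit by visit (protocol)**

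| Visit | Section | Ulcer record |
|---|---|---|
| Screening | 4.9, 5.1, Table 2 | Photographs and tracing |
| Day 0 | 4.9, 5.2, 5.3.1, Table 3 | Photographs and tracing |
| Days 14, 28, 42 | 5.5 | Photographs |
| Month 3, and +14, +28, +42 days | 5.6, 5.6.2 | Photographs |
| Month 6 | 5.7 | Photographs |
| Month 9 and Month 12 | 5.8, 5.10 (both refer to 5.6) | Photographs |
| Months 9 and 12, +14, +28, +42 days | 5.9, 5.12 | Photographs |
| Months 15 and 18 | 5.13, 5.14 | Photographs |
| Before a planned intervention | 5.15 | Photographs |

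No list after Day 0 contains a tracing, a diameter or an area. Protocol 4.9 says that ulcer information goes on the CRF, but it names no dimension. I do not rely on the tracing row of the SAP schedule: that table is incomplete in the text available to me, and its ulcer-photograph row also stops at Day 0 there.

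**2. How sensitive the 20% threshold is without a scale**

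The camera distances below are illustrative assumptions; the documents give none. They suppose the same lens and angle each time.

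- A 20% fall in the product of two diameters, shared equally, multiplies each diameter by √0.80 = 0.894. Each diameter falls by 1 − 0.894 = 10.6%.
- Apparent length varies as 1/distance, so the apparent product varies as 1/distance². An unchanged ulcer looks 20% smaller when the distance is multiplied by 1/0.894 = 1.118, for example 30 cm becoming 33.5 cm.
- Apparent change in the product for an unchanged ulcer, 1/(1 + d)² − 1:

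| Camera farther by d | Apparent change |
|---|---|
| 5% | −9.3% |
| 10% | −17.4% |
| 15% | −24.4% |
| 20% | −30.6% |

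- Weight of one ulcer: 100/10 = 10 points with 10 subjects, and 100/8 = 12.5 points with 8. The step is larger if the denominator is ulcer subjects only; the documents do not fix their number.

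**3. The SAP formula**

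Post-baseline minus baseline is a difference, not a percentage. A product falling from 20 to 16 cm² gives −4 cm². One falling from 2 to 1.6 cm² gives −0.4 cm². Both are 20% reductions, since 4/20 = 0.4/2 = 0.20. The difference has to be divided by baseline before it can be compared with 20%.

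**The case against.** The strongest case on the other side is that little depends on this count. The study is descriptive, and its primary objectives are feasibility, tolerability and safety. The SAP makes the 20% count conditional on data being available. Complete healing is the unconditional ulcer result. Under protocol 5.18 it rests on inspection by the investigator, photographs, a two-week recheck and confirmation by an outside physician, so it needs no scale. A clearly smaller ulcer can also be recognised in serial photographs. All of this stands, and it confines the point to the 20% count and to the qualitative nature of the looser protocol criterion.

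Three stronger readings are tempting, and the documents do not support them.

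- A reader might infer that baseline size comes from the tracing and later size from a photograph. No passage says so. Photographs are also taken at Screening and Day 0, and the SAP applies one diameter rule at both times. What is missing is the stated source.
- A reader might infer that the ulcer photographs have no scale, or that no dimensions were recorded. The documents do not require a scale, but they do not say that none was used. The CRF pages are not among the documents and could hold dimensions.
- A reader might take the SAP's conditional wording as proof that no measurement is planned. It shows only that the SAP allowed for missing data. It does not name a source, reader or method either.

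It can also be said that the SAP was signed as final in March and April 2018, so a change to photography may come too late for enrolled subjects. The documents do not give enrolment status. The SAP part of the fix works either way.

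**Conclusion.** The point holds in a limited form. The protocol schedules tracing only at Screening and Day 0 and requires no scale in any ulcer photograph. No calibrated post-baseline measurement is therefore specified for the SAP's 20% count, and a smaller ulcer under protocol 9.1 item 6 can be judged only qualitatively, with no stated rule. Complete healing and the primary objectives are unaffected, so it would be wrong to say that the ulcer evaluation as a whole cannot be answered.

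The size is that of one conditional, descriptive table. Within it the threshold is fragile: a 10.6% error in each diameter is enough to cross it, and one subject is worth at least 10 points. The first conclusion rests on the protocol's visit lists and Table 3. The camera figures are geometry under assumed distances, not evidence that any picture was misread. This is an inexpensive improvement.

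**What to change.** **Protocol 4.9, Table 2 and Table 3 footnotes (4) and (6).** Require a ruler or scale marker beside the largest ulcer in every ulcer photograph from Screening to Month 18. Alternatively, repeat the existing tracing at Months 6, 12 and 18.

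**SAP 2.5.5.**

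- Name the source and the reader of the diameters, and take baseline and post-baseline values by the same scaled method.
- Divide the difference by baseline so that it is a percentage.
- Replace the conditional opening with a rule: the 20% count includes only subjects with scaled measurements at both times, and where none exist only complete healing is reported. Simply deleting the condition would be unwise, because it could commit the SAP to a table that cannot be produced.

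**Cost.** Either a ruler in pictures already being taken, which sites already do for injection sites, or three short tracings per ulcer subject. The SAP change is a few sentences. If visits are already complete, the SAP change alone remains useful, because it decides before database lock which subjects can be counted.
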